Study Design	
Randomized, multi-center, sham-controlled clinical trial.
 
There are two phases of the study; the primary outcome will be evaluated at the end of phase 1 (first 4 to 8 months). At the primary outcome visit, participants originally assigned to active will end device use and participants originally assigned to sham will switch to active. The switch serves two purposes:
 
 1) to provide participants originally assigned to sham the opportunity to receive the active treatment and 2) to explore the post-outcome effects within treatment group. No statistical comparisons will be performed in Phase 2 to compare treatment groups. 
Note: This is not a crossover design.

Number of Sites	Approximately 40
Endpoint	
Primary Efficacy Outcome:
 
 • Mean change in CST from baseline to primary outcome visit

SUBJECT AREA	DESCRIPTION
	
Key Secondary Efficacy Outcomes: Treatment Group Comparisons
 
 • Mean change in retinal volume from baseline primary outcome visit • Percentage of eyes with CST below OCT machine- and gender-specific threshold for DME at primary outcome visit • Percentage of eyes receiving alternative treatment for DME by primary outcome visit • Percentage of eyes with a ≥ 5 letter loss in visual acuity • Patient compliance • Exploratory assessment of treatment effect after the device is stopped or started (see section 7.10 for more details)

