479 8 months post-randomization (see visit windows below). If the visit is not completed by 8 months,
480 the participant will be instructed to discontinue device use, return the study device as soon as they
481 are able, and study participation will be ended.

482

483 **3.1.3 Post-Outcome Phase**

484 At the 4-month visit, all participants will be unmasked to their treatment group assignment.

485

486 Participants originally assigned to Sham who have not already received alternative DME treatment
487 (see section 3.6) will return the original device and have the option to receive the active treatment
488 group device for the next 4 months.

489

490 Participants originally assigned to Active who have not received alternative treatment will return
491 the original device and have the option to complete the remaining follow-up visits without device
492 use.

493

494 **3.1.4 Device Training**

495 On the day of randomization, a device will be provided to the participant according to their
496 randomized assignment. In order for investigators to remain masked, clinical site coordinators
497 will instruct study participants regarding the proper use of the device. The eyelid must be closed
498 for the duration of the treatment. The participant must turn the device on and it will stop
499 automatically. The study participant will be asked to demonstrate proper use in the office, which
500 will be considered the initial treatment. The participant will be instructed to complete the second
501 treatment that day before bed.

502

503 **3.2 Study Visits and Phone Contacts**

504 A phone call is completed by site personnel within approximately one week of randomization (5
505 to 14 days) to emphasize compliance with device use and answer any questions.

506

507 Scheduled follow-up visits will occur at the following times (time from randomization unless
508 otherwise noted):

509

Visit	Target Date	Target Window (around Target Date)	Allowable Window (around Target Date)
1 Month	4 weeks	± 1 week	± 2 weeks
2 Month	8 weeks	± 1 week	± 2 weeks
3 Month	12 weeks	± 1 week	± 2 weeks
4 Month/Primary Outcome Visit*	16 weeks	± 2 weeks	-4 weeks/+16 weeks
~6 Month/2-month post outcome	8 weeks after 4- Month visit	± 2 weeks	± 4 weeks
~8 Month/4-month post outcome	16 weeks after 4- Month visit	± 2 weeks	-8 weeks/+12 weeks

510

*Key visit

511

512 The goal will be for all participants to complete all scheduled visits. However, participants who

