948 robust variance estimation. Baseline CST and the randomization stratification factor will be
949 included as covariates.

950 The percentage of eyes receiving an alternative treatment for DME before the primary outcome
951 visit will be reported. Only participants receiving alternative treatment or completing the primary
952 outcome visit without receiving alternative treatment will be included. Statistical comparison
953 between treatment groups will not be performed.

954 The percentages of eyes with 5-or-more-letter decrease from randomization at primary outcome
955 visit is a binary variable that will be compared between treatment groups using logistic regression
956 with robust variance estimation. Baseline visual acuity and randomization stratification factor will
957 be included as covariates. The mean change in visual acuity will also be reported; however,
958 statistical comparison between treatment groups for the mean change will not be performed.

959 For each logistic regression analysis, the odds ratio for the treatment group effect, 95% confidence
960 interval, and P value will be presented.

961 **7.9 Safety Analyses**

962 All reportable adverse events will be categorized as study eye or systemic. All events will be
963 tabulated by treatment group in a listing of each reported Medical Dictionary for Regulatory
964 Activities (MedDRA) term and summarized over each MedDRA System Organ Class. All
965 randomized participants will be included in safety analyses.

966 Since there are no known risks of the device, there are no pre-specified safety outcomes of interest.
967 However, the frequency of each ocular adverse event occurring at least once per eye and each
968 systemic event occurring at least once per participant will be calculated.

969 In addition, the following will be tabulated by treatment group:

970 • For each MedDRA System Organ Class, percentage of participants with at least one
971 serious event
972 • Number of adverse events thought by investigator to be related to treatment

973 No formal statistical comparisons will be performed for reported adverse events.

974 **7.10 Outcome Measures Phase 2 (4 Months Post-Outcome)**

975 The following post-switch effects on DME from completion of the 4-month/primary outcome visit
976 to the final visit will be tabulated separately within each treatment group:

977 • Duration of effect on DME after active treatment is stopped

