978 ○ Mean change in CST between 4-month and the final visit
979 ○ Mean change in retinal volume between 4-month and the final visit
980 ○ Percentage of eyes with CST below OCT machine and gender-specific threshold
981 for DME at final visit
982 • Effect on DME in eyes previously receiving sham that switch to active
983 ○ Mean change in CST between 4-month and the final visit
984 ○ Mean change in retinal volume between 4-month and the final visit Percentage of
985 eyes with CST below OCT machine and gender-specific threshold for DME at the
986 final visit
987 • Patient compliance

988 For continuous outcomes, median and interquartile ranges and/or means and standard deviations
989 will be reported to describe the data. Only participants with available CST at the primary outcome
990 visit that did not already receive alternative DME treatment will be included. No statistical
991 comparisons will be performed in Phase 2 to compare treatment groups.

992 **7.11 OCT Angiography Ancillary Study**

993 At a subset of sites with OCT angiography capabilities, images will be taken at baseline and 4
994 months to explore whether there are changes in any features evident on OCT angiography.

995 **7.12 Intervention Adherence**

996 For the primary analyses at the end of Phase 1, adherence will be defined as compliance with
997 device use during the primary outcome phase. An exploratory dose response analysis will be

998 performed to evaluate whether there appears to be an association of compliance (defined as the
999 total number of sessions of the study device use during the primary outcome phase) versus
1000 magnitude of treatment effect (defined as the change in OCT CST from baseline at primary
1001 outcome visit). The distribution of the total number of sessions will be described using summary
1002 statistics and graphical methods. A scatter plot with a regression line will be constructed to
1003 examine for evidence of dose-response, separately for each treatment group. If there is evidence
1004 of a dose-response effect in either or both groups, an analysis of covariance will be performed
1005 including treatment, compliance, and the interaction between treatment group and compliance to
1006 test for evidence that the dose-response effect is limited to the active treatment group. If the
1007 interaction between compliance and treatment group is significant, a stratified analysis will be

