 219 odds ratio for the treatment group effect, 95% confidence interval, and *P* value will be presented.
 220 Note the mean change in visual acuity will be imputed and LOCF values will be applied to eyes
 221 with alternative DME treatment, similar to the primary CST outcome. Statistical comparison

222 between treatment groups for the mean change will be performed using analysis of covariance
223 with adjustment for baseline visual acuity and the randomization stratification factor. In
224 addition, the treatment-group risk difference will be computed with the marginal probabilities
225 from a counterfactual model, and the 95% confidence interval will be estimated using bootstrap
226 resampling using a complete case analysis with LOCF applied to eyes with alternative DME
227 treatment (no imputed values).

228 Patient compliance will be reported separately for completers and non-completers, which is
229 defined as the proportion of prescribed treatment sessions completed. For completers, the
230 denominator will be the total prescribed treatment sessions prior to the primary outcome visit;
231 and for non-completers, the denominator will be the total prescribed treatment sessions up to the
232 time when the study device is returned. Note that for both completers and non-completers, if
233 alternative DME treatment is initiated, the denominator will be the total number of sessions
234 prescribed up to the initiation of the alternative treatment. Statistical comparison between
235 treatment groups will not be performed.

236 **3.0 Outcomes Measures Phase 2 (4 Months Post-Outcome)**

237 Upon completion of Phase 1, only eyes that still meet the original protocol major eligibility
238 criteria for VA and OCT at the primary outcome visit will be included in the analysis for Phase
239 2. A separate table for baseline characteristics will be constructed for Phase 2 participants.
240 Within each treatment group, the following outcomes for evaluating post-switch effects on DME
241 from primary outcome to 4 months post outcome will be reported separately. There will be no
242 formal statistical comparisons of treatment groups. Participants originally assigned to the active
243 group will end device use and participants originally assigned to sham will switch to active.
244 Participants who are not using a device during the post-outcome phase but have not received

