245 alternative treatment will be given the option to continue study visits or end study participation
246 early.

- 247 • Effect on DME after active treatment is stopped (for the initial treated group only)
 - 248 ○ Mean change in CST between the primary outcome and 4 months post outcome
249 visit
 - 250 ○ Mean change in retinal volume between the primary outcome and 4 months post
251 outcome visit
 - 252 ○ Percentage of eyes with CST below OCT machine and gender-specific threshold
253 for DME at 4 months post outcome
- 254 • Effect on DME in eyes previously receiving sham (for the initial sham group only)
 - 255 ○ Mean change in CST between the primary outcome and 4 months post outcome
256 visit
 - 257 ○ Mean change in retinal volume between the primary outcome and 4 months post
258 outcome visit
 - 259 ○ Percentage of eyes with CST below OCT machine and gender-specific threshold
260 for DME at 4 months post outcome

261 • Patient compliance (for the initial sham group only)

262 ○ Proportion of prescribed treatment sessions completed between the primary

263 outcome and 4 months post outcome visit

264 For continuous outcomes, median and interquartile ranges and/or means and standard deviations

265 will be reported to describe the data. For the assessment of CST and retinal volume outcomes,

266 the analysis will include 4-month post-outcome completers without missing data at both the

267 primary outcome and 4-month post-outcome visit, as well as 4-month post-outcome non-

268 completers who receive alternative DME treatment in Phase 2. Missing data will not be imputed

269 for 4-month post-outcome non-completers who do not receive alternative DME treatment. It is

270 recognized there is bias in handling of the analysis cohort by not including non-completers who

271 do not meet the failure criteria for alternative DME treatment. Exploratory analysis will be

272 conducted within each group to test whether the post-switch change is significantly different

273 from zero. Similar to Phase 1, patient compliance will be reported separately for 4-month post-

274 outcome completers and non-completers.

275 **4.0 Intervention Adherence**

276 For the primary analyses at the end of Phase 1, adherence will be defined as compliance with

277 device use during Phase 1. An exploratory dose-response analysis will be performed to evaluate

278 whether there appears to be an association of compliance (defined as the proportion of total

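### SAP 3.0 restricts Phase 2 to eyes still meeting the VA and OCT entry criteria, against Protocol 7.10, so PBM eyes that resolved are left out of the durability analysis

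*SAP*

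**What the plan says.** **Analysis set.** Protocol 7.10 reads: "Only participants with available CST at the primary outcome" "visit that did not already receive alternative DME treatment will be included". It sets no VA or CST level. SAP 3.0 instead admits "only eyes that still meet the original protocol major eligibility" "criteria for VA and OCT at the primary outcome visit will be included in the analysis for Phase" 2. Under Protocol 2.2.2 those criteria are a letter score of at least 79, and CST of at least 290 µm (women) or 305 µm (men) on Cirrus, or 305 and 320 µm on Spectralis.

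**Purpose.** The Protocol Summary (Study Design) gives one aim of the second phase as to "explore the post-outcome effects within treatment group". Protocol 7.10 lists "Duration of effect on DME after active treatment is stopped" as the question for the PBM group.

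**Who stays in follow-up.** Protocol 3.1.3 begins: "Participants originally assigned to Active who have not received alternative treatment will return" the device, and these participants may then complete the remaining visits without it. It attaches no VA or CST condition.

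**Outcomes and test.** SAP 3.0 reports, for each original group, mean change in CST and in retinal volume from the primary visit to 4 months later, and "Percentage of eyes with CST below OCT machine and gender-specific threshold" for DME at the later visit. It adds an exploratory within-group test of the change against zero. The only bias in the Phase 2 cohort that it acknowledges is the omission of certain non-completers.

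**The concern.** The two documents define different Phase 2 cohorts, and no text reconciles them. Three consequences follow from the SAP version.

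1. A PBM eye whose CST has dropped below the cut-off is the clearest anatomic responder, and it is removed. So is an eye that has fallen below 79 letters. Eyes that thinned but stayed above the cut-off are kept. Durability is therefore lost for resolved eyes, not for all responders.
2. If every included eye starts at or above the cut-off, the percentage below it starts at 0%. It can only stay there or rise, so in the PBM group it cannot show loss of resolution.
3. Eyes are chosen for a high primary-visit CST, and change is then measured from that same value. If part of that value is transient, the mean change is pulled downward. After sham-to-active this resembles benefit; after PBM is stopped it masks rebound.

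The pilot is meant to inform whether and how to run a pivotal trial, and persistence of effect bears on that.

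**Working it through.** **What follows from the text alone.** Inclusion requires CST at or above the cut-off; the outcome counts eyes below the threshold. The Phase 2 threshold is taken to be the entry cut-off, the only machine- and sex-specific one in the documents. The two conditions are then complementary, so the starting value is exactly 0%. Consequences 1 and 2 need no model.

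**The plan's own figure.** The documents give none for Phase 2. The Phase 1 size (Protocol 7.3.2) reproduces: 2 × (1.960 + 1.282)² × 50² / 30² = 58.4, so 59 per arm by the normal formula and 60 by the t-test, 120 in total; 120 / 0.90 = 133.3, so 134. This gives the 60 completers per arm used below.

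**Inputs from Protocol 7.3.** Baseline-adjusted SD of CST change 50 µm and mean change −2 µm (both from a laser-treated cohort); PBM effect 30 µm.

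**Assumed inputs.** Population mean CST 0 to 60 µm above the cut-off; between-eye SD 70 to 100 µm; transient share of within-eye change variation 25% to 100%; PBM effect fully lost by the final visit. The VA condition is not modelled.

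**Main model.** CST is a persistent level, with a random step in each phase, plus independent noise at each visit. Eyes are selected on baseline CST at or above the cut-off. The variation is scaled to an adjusted SD of 50 µm, and the sham change is set to −2 µm. PBM eyes are 30 µm lower at the primary visit only. Five mean/SD pairs by four transient shares give 20 scenarios of 2,000,000 draws each.

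| Quantity | Protocol 7.10 cohort | SAP 3.0 cohort |
|---|---|---|
| PBM eyes removed by the OCT condition | 0 | 17–36% (10–21 of 60) |
| Sham eyes removed by the OCT condition | 0 | 8–20% (5–12 of 60) |
| PBM change when the true rebound is +30 µm | +30 µm | +18 to +28 µm |
| PBM % below threshold, primary visit | 17–36% | 0% |
| PBM % below threshold, final visit | 8–24% | 3–8% |
| Sham-to-active change when the switch does nothing | 0 µm | −1 to −7 µm |
| Rejection of zero change in that case (60 eyes) | 5% | 5–15% |

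The excluded PBM eyes rebound by +35 to +61 µm, and 47–71% of them are back above threshold. So where the percentage below threshold truly falls, the SAP table shows a rise from 0%. With a transient share of zero the sham shift is about 0 and the PBM change about +30 µm.

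**Closed-form cross-check.** Treat primary and final CST as bivariate normal, with mean m above the cut-off at the primary visit, SD S and correlation ρ. Selecting on primary-visit CST shifts the mean change by

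−(1 − ρ) × S × φ(m/S) / Φ(m/S), with ρ = √(1 − (50/S)²).

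- S = 60, m = 20: ρ = 0.553; shift = −0.447 × 60 × 0.377 / 0.631 = −16 µm. The share dropped is 1 − 0.631 = 37%. A true +30 µm rebound reads as +14 µm. Since all eyes must average +30, the excluded eyes average (30 − 0.631 × 13.9) / 0.369 = +58 µm.
- S = 80, m = 60: ρ = 0.781; shift = −0.219 × 80 × 0.301 / 0.773 = −7 µm.
- S = 60, ρ = 0.9: −4 µm at m = 20 and −2 µm at m = 60.

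Over m = 20 to 60 and S = 60 to 80, the shift with no true change is −7 to −16 µm and the zero test rejects in 14–44% of trials (7–13% with ρ = 0.9). This form is harsher because every departure from perfect correlation is treated as reverting to the mean. The two models agree on direction, not on size.

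**The case against.** Protocol 7.1 calls its statistical chapter a framework for a later SAP, and Protocol 7.10 is worded as a limit on who is included. A narrower SAP set could be read as refinement. That does not rescue it: the plain reading of 7.10 is a cohort definition, and the SAP replaces it without comment.

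The stakes are low. Phase 2 has no between-group comparison, the zero test is labelled exploratory, and the primary outcome is untouched. The Phase 1 analysis of the percentage below threshold and the separate Phase 2 baseline table make the selection visible. All of this stands and limits the severity. Neither table, however, shows what happened to resolved eyes afterwards.

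Regression to the mean is the weakest part. The CST distribution and transient share are assumed, and the SD comes from laser-treated eyes. A repeat of the main model gave a median sham shift of −3 µm and a median rejection rate of 7%; the upper end needs a transient share near 100%. Because Phase 2 participation is optional, 60 per arm is an upper count; with an assumed 30–40 sham eyes the median rejection rate is 6–6.5%. If regression is slower, with deviations that persist from visit to visit, entry selection alone makes the Protocol cohort drift by −5 to −12 µm, and the SAP filter adds only about −2 to −7 µm. These points stand for the third consequence and leave the first two intact.

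Finally, a still-eligible subset is sensible for eyes switching from sham to active. That is a reason to keep it as a supplement.

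**Conclusion.** The concern holds. SAP 3.0 and Protocol 7.10 define different Phase 2 cohorts, and the SAP version removes the eyes that best answer the durability question.

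That loss rests on the text. The 0% starting point rests on the text plus the inference that the DME threshold is the entry cut-off.

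The bias in mean change requires some transient variation in CST. Its direction is then fixed, but its size is uncertain: about −1 to −7 µm under the main model, and up to −16 µm under the harsher one. The effect of the VA condition is unknown. No claim is made about which way the overall reading of PBM shifts. The fault should be corrected because the remedy is cheap, but it is confined to exploratory results.

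**What to change.** In SAP 3.0:

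- Make the Protocol 7.10 cohort (primary-visit CST available, no alternative DME treatment in Phase 1) the main Phase 2 set.
- Report the percentage below threshold at both the primary and the final visit, and state which threshold is meant.
- For the PBM group, among eyes below threshold at the primary visit, report the proportion still below at the final visit.
- Keep the still-eligible subset, chiefly for sham-to-active eyes, as a labelled supplementary table without a test against zero.
- Present any zero-change test in the main cohort as descriptive, noting that entry selection on CST can leave some regression to the mean there too.

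If the sponsor prefers the restriction, the minimum is to amend Protocol 7.10 to match, give the reason, and still report the below-threshold PBM eyes separately.

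The cost is SAP wording and one extra table; the data are already collected for participants who stay in Phase 2. The drawback is that the sham-to-active summary will include some eyes with no remaining DME.

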Protocol Overview	
 1. Informed consent will be obtained. 2. Study eligibility will be assessed. 3. Prior to randomization, the participant's willingness to proceed into the randomized trial will be confirmed. 4. Eligible eyes (one per participant) will be randomly assigned to photobiomodulation or sham. If a participant has two eligible eyes, the eye with the greatest CST will be selected as the study eye and the non-study eye will be followed to evaluate any potential contralateral effect. 5. Training for at-home use will be performed with the randomized device on the day of randomization. 6. A follow-up phone call is performed at 1 week. 7. Participants will return for a follow-up visit every month for the first ~4 months and then every 2 months for 4 months after the primary outcome. The primary outcome assessment will be at ~4 months. 8. Following the primary outcome assessment, participants in the active group will end device use and participants in the sham group will be given the option to switch to the active treatment for the next 4 months. Participants in both groups who do not continue treatment will be given the option to end study participation after the primary outcome visit. A summary of treatment procedures is included below.

SCHEMATIC OF STUDY DESIGN

SCHEDULE OF STUDY VISITS AND PROCEDURES

	Baseline	1-week Phone Call	Interim Visits (1, 2, 3, 6M)	Primary Outcome and Final Visits	DME Tx Initiation Visit*
Device Training	X				
Randomization	X				
E-ETDRS Best Corrected Visual Acuity [†]	X		X	X	X [‡]
Spectral Domain OCT [§]	X		X	X	X
OCTA [¶]	X			X	
Eye Exam [¶]	X		If Needed	X	X
Blood Pressure	X				
HbA1c ^{**}	X				
Compliance Assessment		X	X	X	

Notes

Testing is only required for the study eye unless otherwise specified below.

*Alternative DME treatment (e.g. anti-VEGF) should not be performed unless protocol criteria are met. If alternative DME treatment is planned at an unscheduled visit, study testing must be completed prior to treatment.

[†]Visual acuity performed on both eyes at each visit, including protocol refraction on both eyes at baseline, 4-month, and final visit, and on the study eye only at all other protocol visits.

[‡]Usual care vision may be used if eye has already been dilated when treatment is planned.

[§]OCT in both eyes at all visits; OCT may be obtained with Zeiss Cirrus or Heidelberg Spectralis OCT machines only.

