1008 performed to evaluate the potential association between compliance and treatment effect within
1009 each treatment group. Model assumptions will be checked, and transformation or categorization
1010 of compliance will be used if there is evidence of non-linearity in the dose response. It is
1011 recognized that the study is not powered to detect a definitive dose-response association existing
1012 only in the active treatment group and that lack of significance is not necessarily an indication that
1013 the association does not exist. It is also recognized that compliance may be affected by both
1014 measured and unmeasured post-randomization factors, including efficacy of masking and
1015 perceived effects of the treatment; hence, the observed dose-response associations may be biased.
1016

1017 If compliance lessens over time during the primary outcome phase, an exploratory analysis will
1018 investigate whether there appears to be any association of compliance versus magnitude of
1019 treatment effect over those months.
1020

1021 For Phase 2, adherence will be evaluated in a similar fashion for those using the device to assess
1022 whether compliance affects the post-switch effect within group, specifically:
1023

- For the initial treated group, whether there is an association between compliance during
1024 phase 1 and duration of treatment effect in phase 2.
- For the initial sham group, whether there is an association between compliance during
1026 phase 2 and treatment effect in phase 2.
1027

1028 In addition, for each phase the effect of text message reminders will be evaluated by assessing
1029 compliance within each treatment group. Compliance will be defined as the total number of
1030 sessions of the study device use during each phase divided by the total number of possible
1031 treatment sessions. This analysis will consist of a comparison between those receiving texts and
1032 those not received texts of mean compliance using analysis of covariance, with adjustment for
1033 treatment. Only participants who have been randomly assigned to receive or not receive text
1034 messages will be included in this analysis.
1035

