330 Adherence in Phase 2 will be evaluated only among eyes participating in Phase 2. The protocol
331 specifies that if alternative treatment is given during Phase 2, participation in the study will be
332 discontinued following next study visit. Missing data will be handled similarly to the Phase 1
333 analysis.

334 In addition, for each phase the effect of text message reminders on compliance will be evaluated
335 using the imputed dataset. Compliance will be defined as the total number of sessions of the
336 study device use during each phase divided by the total number of possible treatment sessions
337 based on visit completion status and alternative DME treatment as noted above; and only
338 participants who have been randomly assigned to receive or not receive text messages will be
339 included in this analysis. This analysis will consist of a comparison of mean compliance between

340 those receiving texts and those not receiving texts using analysis of covariance, and will include
341 treatment, number of days from randomization to the primary outcome visit for Phase 1 (and
342 number of days from the primary outcome to 4 months post outcome visit for Phase 2), and an
343 interaction between treatment group and text message reminders, given it is possible that the
344 participants who are assigned to the control group are less compliant and more likely to ignore
345 text messages. However, it is also recognized that the power for testing the interaction is low in
346 this study due to the limited sample size. If a significant interaction is not present, the analysis
347 will be conducted combining the two treatment groups. If a significant interaction between
348 treatment and text message reminders is present, a stratified analysis will be performed.

349 **5.0 Safety Analysis**

350 All reportable adverse events will be categorized as study eye or systemic. All events will be
351 tabulated by treatment group in a listing of each reported Medical Dictionary for Regulatory
352 Activities (MedDRA) term and summarized over each MedDRA System Organ Class. All
353 randomized participants will be included in safety analyses.

354 Since there are no known risks of the device, there are no pre-specified safety outcomes of
355 interest. However, the frequency of each ocular adverse event occurring at least once per eye and
356 each systemic event occurring at least once per participant will be calculated.

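### SAP 3.0 defines the sham-side Phase 2 post-switch outcomes by original arm, with no condition that the active device was taken, although Protocol 7.10 limits them to eyes that switch

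*SAP*

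**What the plan says.** **Population.** Protocol 7.10 describes the sham-side Phase 2 outcome as "Effect on DME in eyes previously receiving sham that switch to active". SAP 3.0 lists the same three measures (change in CST, change in retinal volume, percentage below the DME threshold) under "Effect on DME in eyes previously receiving sham (for the initial sham group only".

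**The switch is a choice.** Item 8 of the Protocol Overview says that "participants in the sham group will be given the option to switch to the active treatment for the next 4 months". Protocol 3.1.3 likewise says that sham participants who have not had alternative treatment "will return the original device and have the option to receive the active treatment" device.

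**Non-users may remain.** SAP 3.0 has a sentence beginning "Participants who are not using a device during the post-outcome phase but have not received", which lets such participants either continue visits or leave. Protocol 3.2 and 5.5.1 contain the same provision.

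**SAP inclusion rules.** Under SAP 3.0 an eye must still meet the main VA and OCT criteria at the primary outcome visit. For CST and retinal volume it must then either have data at both the primary and final visits or have received alternative DME treatment in Phase 2. The SAP adds an exploratory within-group test of the post-switch change against zero. Protocol 7.10 plans tabulation only.

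**Adherence.** Protocol 7.12 opens its Phase 2 paragraph with "For Phase 2, adherence will be evaluated in a similar fashion for those using the device to assess". SAP 4.0 has instead "Adherence in Phase 2 will be evaluated only among eyes participating in Phase 2. The protocol", with no reference to device use.

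**The concern.** A post-switch change is meaningful only for an eye that switched. The SAP has no rule that removes a sham participant who was unmasked at the primary visit, declined the active device and kept attending. That eye had no active sessions, yet its change between the two visits would be averaged with, and tested alongside, the changes of eyes that used the device.

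One of the two purposes given for the switch in the Protocol Summary is to explore effects after the primary outcome within each group. The Endpoint list adds an exploratory look at what happens when the device is stopped or started. A mean over users and self-selected non-users does not describe what follows starting the device, and a reader of the results could not tell that the two were mixed. Adherence has a related gap: compliance is a proportion of prescribed sessions, and a decliner has none prescribed.

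**Working it through.** **Step 1. Can the two populations differ?** Protocol 7.10 requires original sham assignment and a switch. SAP 3.0 requires original sham assignment, VA/OCT eligibility at the primary visit, and either data at both visits or alternative treatment in Phase 2. A decliner can satisfy every SAP condition and fails the Protocol's. The populations coincide only if no decliner meets the SAP's rules. Decliners who leave at the primary visit, or who drop out later without alternative treatment, are excluded from the CST and retinal volume outcomes under either definition.

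**Step 2. Figures in the documents.** There is no Phase 2 uptake, effect, SD or power. The only planning figures are for the Phase 1 between-group comparison (Protocol 7.3.2): difference 30 microns, SD 50, two-sided 5%, 90% power, 120 eyes raised to 134. These reproduce. The normal approximation gives 2 × (1.960 + 1.282)² × 50² / 30² = 58.4, so 59 per group and 118 in total. The noncentral t calculation gives 60 per group, 120 in total. Allowing for 10% loss, 120 / 0.9 = 133.3, so 134. The concern does not rest on these figures; 30 and 50 are borrowed below only to set a scale.

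**Step 3. Dilution.** Let q be the share of analysed initial-sham eyes that declined, E the mean change in switchers and D the mean change in decliners. The mean under the SAP definition is (1 − q)E + qD. With D = 0 it is (1 − q)E.

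**Step 4. Illustration.** Assumptions: E = 30 microns of reduction, D = 0, within-class SD 50, 60 analysed initial-sham eyes, one-sample two-sided t test at 5%. The SD in the mixed set is √(50² + q(1 − q)E²); at q = 0.4 this is √(2500 + 216) = 52.1. The switchers-only set has 60(1 − q) eyes and SD 50.

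| q | Mean, SAP set | Power, SAP set | Switchers, n | Mean, switchers | Power, switchers |
|---|---|---|---|---|---|
| 10% | 27 | 0.982 | 54 | 30 | 0.991 |
| 20% | 24 | 0.945 | 48 | 30 | 0.983 |
| 30% | 21 | 0.870 | 42 | 30 | 0.967 |
| 40% | 18 | 0.749 | 36 | 30 | 0.938 |

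With E = 15 microns, the SAP set gives means of 13.5, 12, 10.5 and 9 microns and power of 0.536, 0.443, 0.354 and 0.274. Switchers only give 15 microns throughout and power of 0.581, 0.530, 0.476 and 0.417. Under these assumptions, the smaller set costs less power than the dilution does.

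**Step 5. Compliance of a decliner.** SAP 2.2 and 3.0 define compliance as sessions completed over sessions prescribed. For a decliner this is 0/0, which has no value.

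**The case against.** The strongest reply is that the label only names the arm. It mirrors the bullet above it, which is marked for the initially treated group. The surrounding text speaks of post-switch effects and says that sham participants will switch. Protocol 7.12 itself uses initial sham group as shorthand directly after limiting the analysis to device users. On this reading Protocol 7.10 still governs and the SAP is merely terse. The reading is possible, and the authors may have assumed that everyone switches. It does not settle the matter: the SAP states who enters the analysis, that rule has no device condition, and the section itself provides for participants without a device.

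Two further points stand. The exposed group may be small or empty: the explicit route to finish follow-up without a device (Protocol 3.1.3) is written for the active arm, and decliners may leave at the primary visit. An analysis of everyone offered the switch would also be legitimate if labelled as such, but the SAP does not label it so and plans no switchers-only analysis of these outcomes.

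A reader might also infer that decliners will be entered at 0% compliance or imputed as device users. The documents do not say so. The Phase 1 rule that SAP 4.0 carries into Phase 2 treats as missing only eyes lost to follow-up or given alternative treatment, and SAP 8.3 by default keeps only participants with data. A decliner who attends the final visit untreated would most naturally have no compliance value and leave that analysis.

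**Conclusion.** The point holds as a mismatch between Protocol and SAP. Any decliner who meets the SAP's inclusion rules is counted in a change described as post-switch and in its test against zero, contrary to Protocol 7.10. If decliners do not change, the mean is scaled by (1 − q); if they do change, the distortion may differ in size or direction. With q = 0 there is no effect.

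It would be tempting to say that the reported change will fall from 30 microns to 24 or 18. The documents do not support that: no decline rate is given, and 30 microns is a Phase 1 between-group planning difference, not a within-group change after switching. Nor does the Protocol state the purpose of the switch as measuring the effect of starting the device; its wording is broader. The within-group test is uncontrolled, so even in switchers it mixes any device effect with natural change. The primary analysis and the Phase 1 conclusions are untouched. Phase 2 has no between-group comparison, and all of its results are exploratory.

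**What to change.** In SAP 3.0, define the sham-side post-switch outcomes and the within-group test on initial-sham eyes that received the active device at the primary outcome visit. Report the number who declined, and tabulate decliners who stayed in follow-up separately.

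In SAP 4.0, replace the Phase 2 adherence set with the device users named in Protocol 7.12, and state that decliners have no defined compliance. Apply the same set wherever Phase 2 compliance is used, including the text-message comparison.

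The change is to SAP wording, plus an indicator of who received the active device. The documents provided do not confirm that such a field exists: Protocol 4.2 leaves accountability to a coordinator manual. Protocol 8.1 does plan electronic device data files, from which use could be established. The downside is fewer eyes in the exploratory test; if nobody who declined is retained, nothing is lost.
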